**B. Procedures for Sample to Determine Appropriate Dose of Transdermal Estradiol Gel:**

We wish to identify the lowest daily dose of transdermal estradiol gel to achieve plasma estradiol levels between 80 and 120 pg/ml; blood levels of estradiol comparable to those obtained with the previously employed transdermal system in this protocol. We do not expect sustained plasma estradiol levels above this range. Nonetheless, the normal follicular phase range of plasma estradiol is between 60 and 300 pg/ml and it is possible that a single high level of estradiol will be observed depending on how soon after gel application blood samples are obtained. Thus, we will recruit up to 10 women who meet the protocol's selection criteria. Each woman will be administered Lupron for two months only. After the first month of Lupron treatment when ovarian suppression has been achieved, we will administer 2-3 applications (approximately 6.0– 9.0 mg estradiol gel (open label)) once a day for four weeks. Estradiol gel (EstroGel® 0.36% estradiol in a hydroalcoholic absorptive gel base; Ascend Therapeutics, Herndon, VA) is dispensed in a controlled release pump bottle calibrated to provide 1 ml of gel containing 3.0 mg of estradiol per pump. The colorless, odorless, and fast drying gel is applied to the skin over the arms, shoulders and outer thighs (as needed) once each day (usually in the morning). Plasma estradiol levels after use of 3.0 and 6.0 mg daily doses (i.e., 1 and 2 pumps respectively) for 7 days in men were approximately 86 and 125 pg/ml, respectively (137). Thus, we anticipate that plasma estradiol levels should reach approximately 100 pg/ml with the two to three applications proposed in this pilot study. Blood samples will be obtained at weekly clinic visits to evaluate whether this dose administered once a day is sufficient to achieve the plasma

estradiol levels targeted in this study (i.e., 80-120 pg/ml). If after one week of two applications of estradiol gel once a day, we observe that this dose schedule is insufficient to consistently obtain the desired blood levels, we will increase the dose to three applications (9.0 mg) each day for the next three weeks. Alternately, if adequate blood levels are observed after the two applications once a day regimen then women will continue at this dose for the remaining three weeks to evaluate the stability of plasma estradiol levels with the two applications each day regimen. We do not anticipate needing a dose greater than three applications each day. After the four weeks of estradiol treatment, all women will receive one week of progesterone suppositories (200 mg twice a day) to precipitate a progesterone withdrawal-induced menses. Upon completing this evaluation, we will provide the data to the FDA to modify the IND under which this protocol and its companion protocol (90-M-0088) are conducted. The duration of Lupron treatment is a third the length of time in which Lupron is administered in the regular six month protocol and the duration of estradiol treatment is the same as that approved in the original protocol. Women participating in this component of the protocol will not be asked to participate in any of the additional procedures employed in the six month protocol (i.e., brain imaging, IPCs, or metabolomics).

Blood Samples for this component of the protocol (10 ml) will be drawn at each visit, if possible, for the duration of the study (8 weeks). Total blood volume will be 90 ml. All blood sampling will be obtained as described in the core protocol. This blood will then be analyzed for gonadotropins and estradiol.

e) End of Participation

When available, the results of this study will be discussed with each participant. Controls

will be discharged from this protocol with follow-up as needed by their private healthcare provider.

5) Management of Data and Samples:

a. Storage

Samples and data will be stored using codes that we assign. Data will be kept in password-protected computers. Samples will be kept in locked storage. DNA samples and cell lines will be stored in locked freezers in [name]'s laboratory (NIAAA) on [name]. Only study investigators will have access to the samples and data. Upon the completion of the study, blood samples, DNA and cell lines will be retained. Any loss or destruction of samples will be reported to the IRB.

Data from structured diagnostic interviews and symptom ratings are kept in secure research files and electronically on the Branch server space or within the CTDB database. Access to these research files is only available to study investigators. Symptom ratings, diagnostic interviews, and other questionnaires will be collected through an online system using a subject-specific log in and password to protect confidentiality (see Appendix).

b. Data and sample sharing plan

This protocol is not subject to the Genomic Data Sharing (GDS) policy. The sharing of Genomic data according to the GDS policy is covered under the screening protocol 81-M-0126. Data and samples may be shared with dbGaP, collaborating laboratories at NIH or outside of NIH and/or submitted to NIH-designated repositories and databases if consent for sharing was obtained. Repositories receiving data and/or samples from this protocol may be open-access or restricted access.

Samples and data will be stripped of identifiers and may be coded ("de-identified") or

unlinked from an identifying code (“anonymized”). When coded data is shared, the key to the code will not be provided to collaborators, but will remain at NIH. Data and samples may be shared with investigators and institutions with an FWA or operating under the Declaration of Helsinki (DoH) and reported at the time of continuing review. Sharing with investigators without an FWA or not operating under the DoH will be submitted for prospective IRB approval. Submissions to NIH-sponsored or supported databases and repositories will be reported at the time of Continuing Review. Submission to non-NIH sponsored or supported databases and repositories will be submitted for prospective IRB approval.

Required approvals from the collaborating institution will be obtained and materials will be shipped in accordance with NIH and federal regulations.

6) Additional Considerations:

Estradiol gel (EstroGel® 0.36% estradiol in a hydroalcoholic absorptive gel base) is manufactured by Ascend Therapeutics, Herndon, VA. Progesterone suppositories will be manufactured and supplied by the NIH Pharmacy.

7) Risks and Discomforts:

A. Effects of Medications Administered in this Protocol

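### The estradiol gel pilot sets out to find the lowest dose reaching 80-120 pg/ml, but if two applications suffice or overshoot it cannot show that no smaller dose would do

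*Combined protocol and SAP*

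**What the plan says.** Section 4d, Additional Procedures B, gives the objective: "We wish to identify the lowest daily dose of transdermal estradiol gel to achieve plasma estradiol levels between 80 and 120 pg/ml". The doses are fixed in the same section: "we will administer 2-3 applications (approximately 6.0– 9.0 mg estradiol gel (open label)) once a day for four weeks". The pump is "calibrated to provide 1 ml of gel containing 3.0 mg of estradiol per pump", so the available steps are 3.0, 6.0 and 9.0 mg.

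The decision comes after one week on two applications and has two branches. If levels are insufficient, "we will increase the dose to three applications (9.0 mg) each day for the next three weeks". Otherwise, "if adequate blood levels are observed after the two applications once a day regimen then women will continue at this dose". The upper limit is set by expectation: "We do not anticipate needing a dose greater than three applications each day". The section also says that levels are not expected to stay above the target range, and it gives no rule in case they do.

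The supporting exposure data, for 3.0 and 6.0 mg daily, are given as "i.e., 1 and 2 pumps respectively) for 7 days in men were approximately 86 and 125 pg/ml, respectively". From these the section anticipates about 100 pg/ml with two to three applications. On completion, "we will provide the data to the FDA to modify the IND" that covers this protocol and 90-M-0088.

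Two other places bear on the point. Section 1D, Estradiol, items 3 and 4 of the formulation list, reports that an earlier pilot of a 0.06% gel at 0.75-3.0 mg/day did not reach the desired levels consistently in women, and then introduces the present pilot as a trial of a higher dose. Section 3b describes the 10 women as recruited to establish a dose range.

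**The concern.** A lowest adequate dose is shown by two observations: the dose works, and the next step down does not. Here the smallest dose given is the starting dose. If it works, it is the lowest dose in the pilot by construction, and whether a smaller one would also have worked is not observed. If it overshoots, the scheme has nowhere to go, because insufficiency is the only trigger for a change.

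This matters because the pilot is meant to support the estradiol regimen in two protocols. A statement that the lowest adequate dose had been found would carry into both, although in two of the possible outcomes the design did not test it.

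**Working it through.** **Inputs** (all from Section 4d, Additional Procedures B, unless noted)

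- Target: 80-120 pg/ml.
- Doses given: 6.0 mg (two pumps), then 9.0 mg (three pumps) if insufficient. Doses given below 6.0 mg: none.
- Cited levels: 3.0 mg, 86 pg/ml; 6.0 mg, 125 pg/ml.
- Anticipated level at 6.0-9.0 mg: about 100 pg/ml.
- Sample: up to 10 women, with no sample-size calculation and no numerical criterion for adequate or consistent levels. I read adequate as 80-120 pg/ml.

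**Step 1: the plan's own figure.** A straight line through the two cited points has slope (125 - 86)/(6 - 3) = 13 pg/ml per mg and intercept 86 - 13 × 3 = 47. At 9.0 mg it gives 47 + 13 × 9 = 164. A power curve has exponent ln(125/86)/ln 2 = 0.54 and gives 86 × 3^0.54 = about 156 at 9.0 mg. A level of 100 corresponds to (100 - 47)/13 = 4.1 mg on the line and 4.0 mg on the power curve, or 1.3-1.4 pumps. The anticipated 100 pg/ml at 6.0-9.0 mg is not reproduced. At face value, one pump is in range (80 ≤ 86 ≤ 120) and two pumps are just above it (125 > 120).

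**Step 2: how far the cited levels can be pushed.** They are described as levels in men, and the documents do not say whether they include the subjects' own estradiol, which suppressed women would largely lack. Assume that they include an amount b, and subtract it from the line. The documents give no value for b, so I take 0 to 47 pg/ml.

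| Dose | Level | In range when |
|---|---|---|
| 3.0 mg | 86 - b | b ≤ 6 |
| 6.0 mg | 125 - b | 5 ≤ b ≤ 45 |
| 9.0 mg | 164 - b (extrapolated) | b ≥ 44 |

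Within this span any of the three steps can be in range, so the cited levels do not settle whether the untested step would be adequate.

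**Step 3: what each outcome shows.**

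| Result at two | Next | What is shown about the lowest dose |
|---|---|---|
| Below range | Three, in range | Two was too little and three was enough: a lower bound in whole pumps |
| Below range | Three, not in range | No adequate dose among those given |
| In range | Stay at two | Two suffices; the step below is unobserved |
| Above range | No rule | Two overshoots; the step below is unobserved |

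The first row is informative if levels rise with dose. Even there, dose is confounded with time: two applications are judged after one week, while three are observed over weeks 2-4. A level still climbing at one week would look like a dose effect. The section does not say whether the rule applies per woman or to the group; the table reads the same either way.

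**The case against.** The strongest reply is that the step below had already been tried. The 0.06% gel was given to women at up to 3.0 mg/day, the same daily amount as one pump of the present gel, and it did not reach target consistently. Starting at two applications is then a sensible next move. This stands as a likely explanation and as some evidence against doses up to 3.0 mg. It is incomplete: the earlier gel had a different concentration, and Additional Procedures B does not cite the result but instead quotes 86 pg/ml at 3.0 mg. The two sections point in different directions on the same daily amount.

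It can also be said that the working purpose is sufficiency. The section heading speaks of an appropriate dose, and the weekly samples are there to see whether the dose is enough. If two applications hold women at 80-120 pg/ml, they have the intended exposure whether or not less would have done. That is right, and it is why the pilot remains useful. It does not supply the property that the objective names.

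Three stronger readings are tempting, and the documents do not support them.

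- A reader might infer that the pilot can never identify a lowest dose. It can give a whole-pump lower bound when two fail and three succeed.
- A reader might infer from 86 pg/ml that one application is the lowest adequate dose. Step 2 shows that the figures do not settle this, and the earlier gel result points the other way. The source is also unclear: the text says men, while the title of reference 137 names postmenopausal women.
- A reader might infer that an unsupported lowest-dose claim will go to the FDA. The protocol promises only to provide the data.

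**Conclusion.** The objective claims more than the design can deliver. The pilot can show whether two applications suffice or three are needed. Of the four outcomes in Step 3, one (two below range, three in range) shows a lower bound, qualified by the confounding with time on gel. Two (two in range, two above range) leave the lowest adequate dose undetermined by this pilot. The remaining one finds no adequate dose.

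This rests on the text of the decision rule: zero doses below two applications, upward movement only, and no rule above 120 pg/ml. It does not depend on the levels cited in men or on the assumed b. Those serve only to show that the untested step cannot be dismissed on the protocol's own figures. The consequence is limited to an unsupported description of the chosen dose. The pilot's value for choosing between the two tested doses is unaffected.

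**What to change.** Restate the pilot objective, and the report that accompanies the data to the FDA, as whether two applications, or failing that three, give 80-120 pg/ml. Report each woman in one of four classes:

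- (a) two below range, three in range: lower bound shown;
- (b) two in range: lowest dose not determined by this pilot;
- (c) two above range;
- (d) two below range and three not in range, stating whether below or above.

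Do not describe the dose as the lowest effective dose on the strength of women in (b) or (c).

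If the sponsor keeps the lowest-dose objective, Section 1D, Estradiol, and Section 4d, Additional Procedures B, must be reconciled. That covers the earlier 0.06% gel result, the cited levels, the tested range and the missing rule for levels above range. The text should say whether the lower bound is assumed from earlier experience or tested here. The doses and rules are for the sponsor to set.

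Restating the objective costs a few sentences and a weaker claim. It changes no treatment, visit or sample.

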**Lupron**

The most frequent adverse effect of Lupron is hot flushes (flashes) reportedly occurring in 4-89% of patients receiving the drug. Lupron-induced hot flushes have ranged in severity from occasional mild flushing to frequent sweating. In general, episodes of flushing persist with continued therapy in most patients receiving Lupron. In a recently completed study of 400 women of reproductive age with either uterine fibroids or endometriosis who each received 3.75 mg depot Lupron every month for a period of six months, the most common side effects

reported to occur were as follows: 1) hot flashes of mild to moderate intensity (89%), 2) headache (22%), 3) nervousness or irritability (11%), and 4) insomnia (10%). Local irritation at the injection site was complained of in less than 10% of the patients in this sample, and there was a mean decrease in bone density, as measured by bone densitometry, of 3.4 to 4.0%, which totally reversed after the medication had been discontinued for six months. Approximately ten patients of the original sample of 400 found the side effects to be severe enough to discontinue therapy. Regular menstrual cycle function returned within two months following the last injection of depot Lupron (Tapp Pharmaceuticals, personal communication). Blurred vision, lethargy, memory disorder, and numbness have been reported in less than 3% of patients receiving the drug. Thrombophlebitis, phlebitis and/or pulmonary embolism, and congestive heart failure have occurred rarely in patients receiving Lupron, but a causal relationship to the drug has not been established. Adverse GI effects occurring in 2% or more of patients receiving Lupron include nausea and/or vomiting, constipation, and anorexia. Diarrhea and a sour or unusual taste in the mouth have been reported less frequently. Other adverse effects of Lupron occurring in less than 3% of patients include decreased hematocrit and hemoglobin concentration, fatigue, fever, facial swelling, rash, hives, hair loss, and itching. Limited information is available on the acute toxicity of Lupron. Following subcutaneous administration of Lupron in rats at dosages 250-500 times the usual human dosage, dyspnea, decreased activity, and local irritation at the injection site were observed; however, there is no evidence to date that overdosage in humans produces similar adverse effects. Lupron dosages up to 20 mg daily for up to two years have not produced unusual adverse effects in humans. There has been one report of an anaphylactic reaction in a patient following administration of a GnRH agonist. Recent longitudinal follow-up studies of girls and boys receiving GnRH agonists as a treatment for

precocious puberty report the development of normal reproductive function and fertility (138-140). The FDA recently published a caution about the effects of GnRH agonists in elderly males; however, the safe use of these agents in younger adults and children (141) was not questioned in the FDA statement.

### **Estradiol**

Nausea is the most common side effect of estrogen administration. At conventional replacement doses, higher than those employed in this protocol, this complaint seldom interferes with eating, and no weight loss has been reported. Breast engorgement, endometrial hyperplasia and bleeding are also common side effects of estrogen administration. Pre-existing fibroid tumors of the uterus may enlarge under the effects of estrogen; however, at the dosage and for the duration of estrogen administration in this protocol this risk is small.

The relationship between estrogen, both endogenous and exogenous, and the development of endometrial carcinoma has been suggested by several different lines of investigation (142). Numerous retrospective case control studies published since 1975 have indicated that post menopausal exposure to unopposed estrogens for more than one year results in a two to 12 fold increased relative risk for endometrial cancer. A relationship between the dose and duration of estrogen use and the risk for endometrial cancer has also been shown, the risk being increased after one to four years of estrogen use and rising also with the dosage employed. However, the addition of progesterone to estrogen therapy appears to decrease the risk of endometrial hyperplasia and endometrial cancer to equal or below that of women receiving no hormonal treatment. Recent studies suggest that the optimal regimen to prevent hyperplasia and thus, inferentially, the risk of carcinoma, consists of 12 to 13 days of progestin treatment each month when estrogens are administered (143). There is an increase in thromboembolism and stroke in

women receiving estrogen therapy (144-151) (and, possibly, ovarian cancer (152) and lung cancer (153, 154)); however, these complications are unlikely at the dose and duration of estrogen therapy employed in this protocol and in the younger age of the women participating in this trial. One study (123) reported no effect of the estrogen patch on the four clotting indices previously shown to be altered by oral contraceptive use (143, 155, 156). Additionally, recent studies (151, 157, 158) observed that an increased risk of venous thromboembolism was associated with oral but not transdermal estrogen compared with nonusers (in one study (157) odds ratios = .42 [95% CI, 1.5 to 11.6] and 0.9 [95% CI, 0.4 to 2.1] respectively). The mechanism underlying this observed difference in the risk of thromboembolism is not known; however, it has been suggested to reflect a lower activation of hepatic metabolism by the transdermal route of administration due to a smaller first pass effect. Blood pressure, on average, appears to be unaffected by estrogen therapy, although both increases and decreases have been reported. Post menopausal estrogen therapy has been observed to increase the relative risk of cardiovascular disease in some (148, 159) but not all studies (160-162). Indeed recent analyses of the Women's Health Initiative demonstrate that the adverse effects of estrogen therapy on cardiovascular outcomes were largely confined to older women compared with younger perimenopausal women (150, 163-171). High doses of oral estrogens have been reported to elevate hepatocellular enzyme levels and, less commonly, cause cholestatic jaundice. The risk for gall stones and hepatocellular adenomas has been reported to be increased in association with oral contraceptive use, and although uncommon these complications may also occur with the use of replacement doses of estrogen (172-174). Further, most studies have suggested an increased relative risk of breast cancer after four or five years' use (150, 175-187),

similar to the risk expected if the onset of menopause was delayed for a comparable length of time.

Due to the publicity surrounding the cancellation of the treatment arm of the Women's Health Initiative study (188) that involved the administration of combined conjugated estrogens and medroxyprogesterone acetate (Prempro), we have included the following statement in the consent documents:

Adverse Events Related to Combined Hormone Replacement and the Results of the Women's Health Initiative (WHI):

The WHI study demonstrated that continuous administration of one form of estrogen (conjugated estrogens) in combination with one form of progesterone (medroxyprogesterone acetate) is associated with an increased risk of dementia, heart attacks, stroke, blood clots, and breast cancer. Estradiol, the form of estrogen that we use in this study, is administered as a sole agent (with the exception of one week's combination with progesterone) and, consequently, we do not expect that it will pose the increased risks observed with the chronic combination of the conjugated estrogens and medroxyprogesterone administered in the WHI study. Indeed, while the estrogen alone arm of the WHI trial was shown to be associated with an increased risk of stroke, no increased risk of either heart disease or breast cancer was observed (188, 189).

Estrogens may precipitate migraine headaches, and depression has also been reported to occur with the use of estrogens. In general, considering the dose and duration of treatment that we propose to use in this protocol, the risk of developing such side effects is negligible.

### **Progesterone**

Progesterone and the synthetic progestins are widely prescribed, with indications including dysfunctional uterine bleeding, endometriosis, mastodynia, galactorrhea, and precocious puberty

(128). Side effects reported in women taking progestins are uncommon but may include breakthrough bleeding, edema, change in weight (increase or decrease), cholestatic jaundice, rash (with or without pruritus), depression of mood, easy fatigue, lack of initiative, and chloasma. Since progestins are often used in women with antecedent menstrual irregularity, it is not clear whether the breakthrough bleeding represents an effect of the medication or refractoriness to treatment. In the large majority of patients, menstruation occurs predictably following withdrawal of progestins and is usually more regular than in spontaneous cycles.

For the sake of completeness, it is also notable that side effects have been observed in women receiving combined oral contraceptives, including nausea, breast soreness, vaginal discharge, fluid retention, hypertension, and clotting abnormalities, which have been associated with the estrogen component of the oral contraceptive. Thromboembolic disorders including thrombophlebitis, pulmonary embolism, and cerebral and coronary thrombosis appear to occur with greater frequency in women taking oral contraceptives. While the increased incidence of these disorders has been associated with the estrogen component of the oral contraceptives, it is now believed that the progestogen component may, to a lesser extent, contribute to the increased risk. There are relatively few reports associating oral contraceptives with the development of carcinomas (vaginal, uterine, hepatic, and mammary) despite the vast use of these agents, although this may reflect the latent period needed for cellular transformation. Finally, several reports suggest an association between intrauterine exposure to female sex hormones and congenital anomalies.

